3.6.1. Collections of bacterial biofilm samples

Supra- and subgingival biofilm samples will be taken from the mesial sulci/pouches with Gracey Curettes, minifive type 11-12 sterile. They will be positioned in the most apical portion of the sites and in a single scraping movement in the apic-coronal direction they will be collected. Samples will be deposited in 1.5 ml polypropylene tubes containing 100µl of TE RNase-free solution (10mM Tris-HCl, 0.1mM EDTA, pH 7.6). The collected material will be stored at a temperature of -80^oC, for a maximum of 48 hours, when the total nucleic acids (ANT) will be extracted.

3.6.2. Microbiological monitoring

3.6.2.1. Extraction of Total Nucleic Acids

The ANT of the samples will be extracted using the Epicentre Masterpure DNA & RNA Purification kit (Epicentre, Madison, WI, USA) according to the manufacturer's instructions. Initially, the surfaces of the benches and apparatus will be treated with ribonuclease inhibitors (RNaseAWAY[®] – Invitrogen, San Diego, CA, USA) to minimize the risk of nucleic acid degradation. The tube containing the sample will be taken out of the freezer at -80^oC and kept on ice for 10 minutes for thawing. The collection tube will be shaken in the vortex for 1 minute and the solution will be transferred to a new tube. For the lysis of the collected material, 1.0µL of proteinase K solution (50µg/µL) will be added to the 100µL of the sample's TE solution, and then it will be incubated at 65^oC for 15 minutes. The samples will be kept on ice for 5 minutes, 175µL MCP reagent will be added for protein precipitation and centrifugation for 10 minutes at 12^oC. The supernatant will be transferred to a new tube where 500 µL of isopropanol will be added, the tubes will be stirred for 2 minutes and will be subjected to new centrifugation for 10 minutes at 4^oC. The isopropanol will be discarded and the pellets will be washed twice with 70% ethanol. The pellets will be dried for 10 minutes and then resuspended in 25 µL TE and stored at -80^oC.

3.6.2.2 Preparation of the probes 16S rRNA

Oligonucleotide probes for species not yet cultured should have about 18-22 nucleotides and minimal secondary structures in the conserved region of the 16S rRNA gene for prokaryotic organisms. The sequence of the probes was kindly provided by [name] and has recently been published (PREZA et al., 2009). All probes will be checked in the *Ribosomal Database Project* (<http://rdp.cme.msu.edu/probematch/search.jsp>) system and subsequently synthesized (Invitrogen, São Paulo, SP, Brazil). The controls will consist of sequences complementary to the probes. The probes will be labeled with digoxigenin using a specific oligonucleotide kit, according to the manufacturer's specifications at the final concentration of 4.5pM/µL (DIG Oligonucleotide 3'- End labeling kit, 2nd Generation – Roche, Indianapolis, IN, USA). In general, 100 M of the probe will be added to a sterile 200µL tube pfor a final volume of 10µL. Subsequently, 4µL of a buffer solution, 4µL of a 5mM solution of CoCL₂ , 1µL of a 0.05mM solution of DIG-ddUTP and 1µL of the transferase enzyme (20U/µL) will be added. This solution will be incubated at 37°C for 30 minutes. Subsequently, the solution will be withdrawn and placed on ice for 5 minutes and 2µL of a 0.2mM EDTA solution (pH 8.0) will be added to stop the reaction.

3.6.2.3. *Collection of crevicular fluid samples Liquid chromatography coupled to Tandem mass spectrometry LC-MS/MS (Proteome)*

Gingival and peri-implant fluid samples will be collected at the same sites and at the same time as the sites selected for the bacterial sample (see item 3.8.1 *Collection of bacterial biofilm samples*). The selected periodontal and peri-implant sites will be isolated with cotton rollers and dried with an air jet so that there is an influx of gingival fluid. The samples will be collected using standardized sterile strips of paper (PerioPaper, Oraflow, Smithtown, NY), gently introduced into the gingival and peri-implant sulcus, until they meet resistance, and held in position for 30 seconds, and then transferred to a 1.5mL dry plastic tube. The samples will then be immediately frozen at -80°C until they are processed.

Liquid chromatography coupled to tandem mass spectrometry will be performed in periods 0, 3, 7, 14, 21, 42 and 60 days. The elution of the adsorbed protein will be performed according to a previous protocol (Siqueira and Oppenheim 2009). The sample set will be vortex-stirred for 1 min, sonicated at 7W (4°C for 5 min, vortex-stirred for 1 min, and stored at -80°C . Then, the samples will be lyophilized and resuspended in 50 ml of urea (8 M). The Bradford method will use samples for total protein quantification, using bovine serum albumin (BSA) as standard. The proteins will be reduced, alkylated and digested with trypsin (1:50 w/w-1), and the extracted proteins will be subjected to LC-MS/MS. The samples will be dried in a vacuum concentrator and reconstituted in 22.5ul of 0.1% formic acid. A 4.5ul aliquot containing 2 mg peptides will be analyzed in an LTQ Orbitrap Velos mass spectrometer connected to the EASY-nLC system through a Proxeon ion nanoelectrospray source. The peptides will be separated by a gradient of 2-90% acetonitrile in 0.1% formic acid in an analytical PicoFrit column (20 cm ID75 lm, particle size 5 lm) at a flow rate of 300 ml min-1 over 27 min. The voltage of the nanoelectrospray will be adjusted to 2.2 kV, and the temperature of the source will be 275°C . All instrument methods will be configured in data-dependent acquisition mode. After accumulation, full-scan MS spectra (m/z 300-1,600) will be acquired on the Orbitrap analyzer for a target value of 1 106. The resolution in Orbitrap will be set to r.60,000 and the 20 most intense peptide ions with charge states will be isolated sequentially to a target value of 5,000 and fragmented in the linear ion trap by low energy CID (normalized collision energy of 35%). The signal threshold to trigger an MS/MS event will be set to 1,000 counts. A dynamic delete will be enabled with a deletion size list of 500, a deletion duration of 60 s, and a retry count of 1. A q.0.25 activation and a 10ms activation time will be used. Each sample will be subjected to three readings. Acquired peptide sequences will be identified using MaxQuant software (v.1.3.0.3) and the Uniprot Human Protein Database. With the Perseus v.1.5 application software, the list of identified peptides will be filtered by a minimum localization probability of 0.75, and reverse entries and contaminants will be excluded from further analysis.

The influence of the gingival tissue of the implants and the comparison of the periodontal and peri-implant tissues will be analyzed and compared with the proteomic profile to identify the unique/exclusive proteins adsorbed in each group. A Venn diagram will be constructed to show the differences between the groups. The

Uniprot database will also verify the molecular function and biological process in which the identified proteins are involved. Each group will be characterized according to the ten molecular procedures and biological processes with the most proteins. Heatmaps will be used to show the intensity of LFQ (protein intensity/expression) for each protein identified according to the groups.

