3.2. Sample selection

This clinical study will be submitted for approval by the Ethics

Committee of the University of Guarulhos (CEP-UnG). The 40 individuals will be recruited and evaluated at the Implantology clinic of the University of Guarulhos and must need 2 implants adjacent to teeth, in the same hemiarch. This sample was obtained according to the power test so that the study had a sampling power of 85%, and was therefore subject to subsequent publication in an impactful journal.

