3.6. Obtaining samples

Samples of bacterial biofilm and crevicular gingival fluid (CGF) will be collected at baseline (day 0), and at 3, 7, 14, 21, 42 and 60 days on the mesial surface of the selected tooth and implant sites.

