In addition, the study participant will receive verbally and also in writing the Informed Consent Form (ICF; Appendix I: Informed Consent Form) the recommendation to contact the principal investigator in case of the occurrence of any undesirable effect. If necessary, the researcher will make the decision to resume oral brushing in the 3 sites evaluated (2 implants and 1 tooth) and in this case, the participant will be immediately removed from the study, without prejudice to the basic treatment of hygiene or prosthetic restorations of the implants (receiving the crowns/teeth), that is, they will continue to receive this treatment free of charge. Participants will be followed up until the end stipulated by the research. After this period, participants will be instructed to look for the Clinical Studies Center of the Dentistry course at Univeritas-UNG University or specialized centers in Implantology, if they need any assistance. This return protocol will be the same used for other patients in specialization courses.

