5. BUDGET

Budget proposal: This study is sponsored by the partner companies *Plenum (Brazil)* and MagDent (Israel) in addition to the CNPq grant that will allow the acquisition of inputs after approval by the Research Ethics Committee of Univeritas-UNG University.

COST TABLE

Area of analysis	VALUE (reais)
Clinical, Surgical (implants and healers) and prostheses (funded by Plenum Bioengenharia, Jundiaí, SP, Brazil)	R\$ 90,000.00
Microbiological (funded by Magdent, Israel)	R\$ 250,000.00
Proteome (funded by MagDent, Israel)	R\$ 250,000.00
Medicines (including anti-inflammatory and antihistamine drugs, analgesics) and acetate plates (funded by CNPq Project 311368/2019-0)	R\$ 2.0000,00
Transportation (10 visits x 40 patients x R\$ 10.00 + 15% of the amount allocated to possible complications + Light food/snack R\$ 10.00) (funded by the CNPq Project 311368/2019-0)	R\$ 8.600,00
Total Value	R\$ 600,600.00

6. **SCHEDULE**

STEP IDENTIFICATION	START (dd/mm/yyyy)	TERM (dd/mm/yyyy)
Patient selection	01/03/2025	01/05/2025
Clinical evaluation/implants	01/03/2025	01/06/2025
Treatment	30/05/2025	20/08/2025
Maintenance	05/08/2025	05/10/2025
Microbiome/Proteome	05/08/2025	05/02/2026
Analysis of the results	10/10/2025	05/04/2026
Preparation of publications	10/10/2025	05/05/2026
Final report	10/10/2025	10/05/2026

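### The label-free proteome has no injection order or batch rule, so instrument drift could be mistaken for the visit time course

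*Combined protocol and SAP*

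**What the plan says.** Crevicular fluid is collected "at baseline (day 0), and at 3, 7, 14, 21, 42 and 60 days" from the tooth and implant sites (section 3.6). Each participant contributes three sites, one tooth and two implants (section 4.1.2), and the sample is 40 people (section 3.2).

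For the proteome, section 3.6.2.3 has one scheduling sentence: "Liquid chromatography coupled to tandem mass spectrometry will be performed in periods 0, 3, 7, 14, 21, 42 and 60 days". It adds "Each sample will be subjected to three readings" and a 27-minute gradient. On storage it says "The samples will then be immediately frozen at -80°C until they are processed". Quantification is label-free and is reported by group: "Heatmaps will be used to show the intensity of LFQ (protein intensity/expression) for each protein identified according to the groups". Proteins exclusive to a group are listed and shown in a Venn diagram.

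The schedule in section 6 gives the laboratory work its own line: "Microbiome/Proteome 05/08/2025 05/02/2026".

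Neither section 3.6.2.3 nor section 7 states a run order, a definition of batch, masking of the laboratory to site or visit, or a batch term. The only randomisation in the plan decides which implant receives which healer (sections 3.1 and 3.5.1).

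**The concern.** The objective in section 2 is how the host response evolves while inflammation is induced and progresses, which is a change across visits. Label-free intensities from different runs are compared directly, so a change in instrument sensitivity between runs enters the comparison.

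If early visits are run first, such a change points the same way in every participant. It does not shrink as the sample grows, and where visit and run time coincide no later model can separate them. Normalisation of label-free intensities removes an overall shift, but not drift specific to a protein or the loss of weak signals. The lists of exclusive proteins depend on detection and are open to the second of these.

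The calendar makes an early-visits-first order plausible. The laboratory opens on 05/08/2025, while later participants are still being sampled.

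**Working it through.** The documents give no run count, acquisition time or batch size, so there is no figure of theirs to reproduce.

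**Volume of acquisition** (inputs from sections 3.2, 3.6, 3.6.2.3 and 4.1.2)
- Strips: 40 × 3 sites × 7 visits = 840.
- Readings: 840 × 3 = 2,520.
- Gradient time: 2,520 × 27 min = 68,040 min = 1,134 h = 47.25 days.
- Assumed dropout of 10% or 20% gives 42.5 or 37.8 days.
- Assumed overhead of 10, 20 or 30 min per reading gives 64.8, 82.3 or 99.8 days.

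**Calendar** (sections 3.1 and 6)
- Earliest day 60: 01/03/2025 + 30 days' preparation + 60 + 60 = 29/07/2025.
- Latest day 60: last implant date 01/06/2025 + 60 + 60 = 29/09/2025. That participant's day 0 is 31/07/2025, so only the day-0 and day-3 strips exist when the laboratory opens.
- Window left after the latest day 60: 29/09/2025 to 05/02/2026 = 129 days.

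**Overlap of visit with run position** (share of run-position variance explained by visit)
- Run by period: seven equal blocks of 360 readings, 360 × 27 min = 6.75 days each. The share is 1 − 1/7² = 98.0%. Block midpoints for day 0 and day 21 lie 4 × 6.75 = 27 days apart, and for day 0 and day 60 they lie 6 × 6.75 = 40.5 days apart.
- Run in order of collection date: about half in simulation, if implant dates are assumed uniform from 31/03/2025 (01/03/2025 plus the 30 days' preparation) to 01/06/2025. With dates uniform from 01/03/2025 it is about a third.
- All strips randomised together: about 0.7% on average (500 simulated orders).
- Randomised inside participant blocks of 21 × 3 = 63 readings (63 × 27 min = 28.35 h): under 0.001%.

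**What a shift would do to a paired test of a later visit against day 0**

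Take no true change and a drift that moves the mean within-person change by δ standard deviations of that change. With n = 40 and a two-sided 5% test, the statistic is noncentral t with 39 degrees of freedom and noncentrality δ√40. The critical value is 2.023.

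| Assumed δ | δ√40 | False rejection |
|---|---|---|
| 0.1 | 0.63 | 9% |
| 0.2 | 1.26 | 23% |
| 0.3 | 1.90 | 46% |
| 0.5 | 3.16 | 87% |

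The documents supply no value of δ.

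**The case against.** The strongest reply is that the sentence on periods only lists which sampling days are analysed. Its days are the collection days of section 3.6. Samples are frozen until processed, and the laboratory has a separate window, so a mixed order is feasible. This stands. A reader might infer that the plan prescribes one batch per visit, but the documents do not say so. The defect is an uncontrolled order.

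Three further limits also stand.

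- **The readings.** The plan does not say that the three readings of a strip are consecutive, so it cannot be asserted that they all share one instrument state.
- **The comparisons.** The proteome text compares groups, and section 7 compares gingivitis with mucositis in the different periods. Read as same-visit contrasts, these lose any shift common to the visit. It is tempting to conclude that the PEMF comparison is biased, but that needs a systematic site order as well, and site order is equally unstated. Changes over time remain within scope, because the objective concerns progression and section 7 provides tests for dependent samples.
- **The percentages.** The shifts are assumed, and drift would differ between proteins. The table is not a forecast of the share of proteins wrongly declared changed.

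The reply does not show that the omission is harmless. Both obvious default orders, by period and by availability, tend to put early visits first.

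**Conclusion.** The concern holds as an unspecified run order with a foreseeable consequence. It is not a documented confounding of visit with batch. Run by period, visit and run position are almost wholly aliased (98%). Run as strips become available, they are partly aliased, by roughly a third to a half under the assumed implant dates. The time course is what is at risk.

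The figure of about 47 days should not be read as a minimum. It assumes 40 completers, every strip run singly, one gradient per reading and no overhead. Dropout or pooling lowers it, and overhead raises it. The false-rejection rates of 9% to 87% are illustrative. They apply to one protein with the stated shift, tested against day 0.

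This should be settled before the first strip is run, because aliasing of this kind cannot be undone in the analysis.

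**What to change.** Replace the scheduling sentence in section 3.6.2.3 with text to this effect:

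*Fluid strips from days 0, 3, 7, 14, 21, 42 and 60 are kept at -80°C until the participant's last visit. All 21 strips of a participant are then prepared together and acquired in one block, under laboratory codes that hide site and visit. The block consists of three passes, each containing every strip once in a fresh random order across visit and site. The three readings are averaged to one value per strip before any test.*

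Keeping the passes inside the block means that every site and visit contrast within a person falls in about 28 hours of gradient time. Drift between blocks is then largely shared by both sides of the contrast. Comparisons between participants are not protected in this way.

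The cost is a randomised, coded run list, with no added samples or readings. Acquisition for a participant waits until day 60. Even if all of it waited for the last participant, 47 days of gradient time would fit in the 129 days left, and so would 99.8 days with an assumed 30 minutes' overhead per reading, provided the instrument is available. Day-0 strips would be stored up to 60 days longer than day-60 strips, so storage time differs by visit. That should be reported as a limitation.

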3. MATERIAL AND METHODS

3.1. Experimental design

This prospective, controlled study will induce experimental gingivitis and mucositis in humans using the suspension of hygiene of the elements involved in the research: one tooth and 2 implants. The model used will be one in which only the teeth and implants involved in the research will not be cleaned while the entire oral cavity of

the study participant will be cleaned. To this end, the participants will be molded and will receive an acetate plate that will cover the teeth involved in the research, protecting them from the toothbrush. Participants selected for the study must sign the Informed Consent Form (ICF) after verbal and written explanation of the project. Subjects will receive oral hygiene instruction and biweekly professional prophylaxis within 30 days prior to implant placement. The implants will be installed in time -60 days. After 60 days, that is, at time 0, the healers will be installed in the two implants, one being a conventional healer and the other with an electromagnetic pulse. At the same time, everyone will receive acetate plates to protect the selected areas (tooth and implant) during brushing, to be used for 21 days. Periodontal clinical examination, microbiological (supragingival and subgingival biofilm) and immunological (crevicular fluid) collections will be obtained at times 0, 3, 7, 14, 21, 42 and 60 days. The choice between the implant that will receive the conventional healer or the one with electromagnetic pulse will be made randomly, by means of a randomization table. At the end of the study, they will again receive professional prophylaxis and control of oral biofilm after the experiment. Figure 1 shows the study design.

[figure not shown]

Figure 1. Study design.

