3.3. Sample inclusion criteria

The sample will include 40 systemically healthy individuals, over 18 years of age, who have at least 2 contiguous edentulous spaces; more than 15 dental elements in the oral cavity; have not undergone periodontal treatment for at least 6 months prior to the beginning of the study; agree to participate in the study and agree to sign the ICF.

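### The proteome's only functional summary, the ten annotation terms with the most proteins, favours large generic terms and would miss a PEMF effect on smaller ones; exclusive-protein calls also need equal sampling and a detection rule

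*Combined protocol and SAP*

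**What the plan says.** The proteomic comparison is described at the end of section 3.6.2.3 (crevicular fluid and LC-MS/MS). It has four parts:

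- Profiles are compared "to identify the unique/exclusive proteins adsorbed in each group".
- Presence or absence is displayed graphically: "A Venn diagram will be constructed to show the differences between the groups".
- All identified proteins are annotated: "Uniprot database will also verify the molecular function and biological process in which the identified proteins are involved". The functional summary then follows from those annotations: "Each group will be characterized according to the ten molecular procedures and biological processes with the most proteins".
- Abundance is displayed protein by protein: "Heatmaps will be used to show the intensity of LFQ (protein intensity/expression) for each protein identified according to the groups".

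None of the four has a stated test, background set, participant-level unit or multiplicity rule. Section 7 lists general paired and unpaired tests at a 0.05 level but does not tie them to the proteome.

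The groups are not defined for these displays. Section 3.6.2.3 speaks of periodontal and peri-implant tissues, and section 7 of gingivitis and mucositis groups. The design in section 3.1 has three sites per person, "the suspension of hygiene of the elements involved in the research: one tooth and 2 implants", and "the healers will be installed in the two implants, one being a conventional healer and the other with an electromagnetic pulse". Section 3.3 sets the size: "The sample will include 40 systemically healthy individuals".

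**The concern.** Proteomics is in the study title and in the objective (section 2), and the top-ten list is the only step that turns protein identifications into biology. A count of identified proteins per term is highest for broad terms, whichever group is examined. Two groups can therefore show nearly the same list while a narrow pathway has switched off in one of them. The reader of such lists would conclude that PEMF left the host response unchanged.

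The exclusive-protein list has a different weakness. A protein counts as present once it is found, so a rarely detected protein can fall on one side by chance. If both implants are pooled as mucositis and set against one tooth, the implant side has twice as many chances, and the excess could be read as a richer peri-implant proteome.

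**Working it through.** The plan gives no figure to reproduce here, and no protein count, term count or detection rate. Everything below except the strip counts rests on stated assumptions.

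**1. Strips by design.** 40 participants × 7 visits = 280 per site type; × 3 sites = 840; × 3 readings (section 3.6.2.3) = 2,520 readings. PEMF v conventional is 280 v 280. Both implants pooled against the tooth is 560 v 280 overall, or 80 v 40 at one visit.

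**2. Small illustration of the top-ten list.** Assumptions: 500 detected proteins; 200 terms with sizes log-uniform on 3 to 250; each group a random 400 of the 500; 1,000 runs. Two groups with no true difference share 9.2 of ten terms on average, and the tenth term holds about 160 proteins. A 12-protein term contributes at most 12, so it cannot enter the list even if it is fully present in one group and 3 of 12 in the other.

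**3. Second model.** Assumptions: 2,000 detectable proteins; 300 overlapping terms with log-normal sizes of about 5 to 500 and random membership; per-strip detection logit normal with mean −6 and SD 2.5; 300 runs per scenario. The affected term is either one of the ten largest or of size rank 31 to 60.

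| Scenario | Terms shared (of 10) | Affected term enters or leaves a list |
|---|---|---|
| No effect, 280 v 280 strips | 9.35 | 6% |
| No effect, 280 v 560 strips | 9.37 | 8% |
| PEMF removes 30% of a ten-largest term | 9.02 | 42% |
| removes 50% | 8.90 | 70% |
| removes 80% | 8.69 | 91% |
| removes 100% | 8.60 | 94% |
| removes 50% of a rank 31–60 term | 9.23 | 0% |
| removes 100% of a rank 31–60 term | 9.20 | 0% |

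The rank correlation of raw count with term size is about 0.97. For the rank 31–60 term, a direct Fisher comparison of the two groups gives p<0.05 in 73% (half lost) and 100% (all lost) of runs. That comparator tests one term chosen in advance and ignores clustering by participant. It shows only that the information is in the files and the ranking discards it.

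**4. Exclusive calls with pooled implants.** Let p be the chance of detecting a protein on one strip, equal at all sites and independent between strips. With n tooth strips and 2n implant strips, a = 1−(1−p)^n and b = 1−(1−p)^(2n). The false implant-exclusive probability is b(1−a); the false tooth-exclusive probability is a(1−b).

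At one visit (n = 40):
- p = 0.5%: a = 0.182, b = 0.330, giving 27% v 12% (2.2-fold).
- p = 2%: a = 0.554, b = 0.801, giving 36% v 11% (3.2-fold).
- p = 5%: a = 0.871, b = 0.983, giving 13% v 1.4% (8.8-fold).

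Across all seven visits (n = 280):
- p = 0.5%: 23% v 5%.
- p = 1%: 6% v 0.3%.
- p = 2%: 0.35% v about 0%.

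**5. Equal strips.** With 40 v 40 strips at p = 2%, a protein is called exclusive to one side or the other with probability 2a(1−a) = 2 × 0.554 × 0.446 = 49%. This is symmetric noise, not bias. If a protein must be found in at least 8 of 40 participants at a visit, a 2% protein qualifies with binomial probability of about 1 in a million. If detection at any of seven visits counted, the per-participant chance would be 1−0.98^7 = 13%, and it would qualify about 15% of the time. The rule therefore has to be set per visit.

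**The case against.** The list is descriptive: groups are characterised by it, and no p-value or decision rests on it. The same section plans a Venn diagram and per-protein LFQ heatmaps, where a change in a dozen proteins could appear, and section 7 provides paired tests. This lowers the severity but does not remove the point. The diagram and the heatmaps have no stated test, section 7 does not link its tests to them, and neither summarises function.

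A reader might infer that the lists will look alike whatever PEMF does. That is not supported: losing half of a ten-largest term moves it in or out of a list in 70% of runs, and losing all of it in 94%.

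A reader might also infer that the number of strips drives the ranking. Doubling the strips on one side raised the proteins found from about 1,047 to 1,245 but left 9.37 terms shared, against 9.35. Nor is the ranking purely by database size, because only identified proteins are counted and detectability in the fluid matters too.

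Finally, unequal sampling does not touch PEMF v conventional. Each participant has one implant of each kind, sampled at the same visits, and section 4.1.2 removes the whole participant when brushing is resumed. The 2:1 imbalance arises only if the implants are pooled, which the plan neither states nor rules out.

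**Conclusion.** The concern holds in a limited form, as a change that should be made rather than a flaw that invalidates the study. The top-ten count is insensitive to a PEMF effect on small or mid-sized terms. Two models with different assumptions agree on this, although the near-perfect correlation with term size follows partly from assigning proteins to terms at random. A large effect on a leading term could still be seen.

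The bias in exclusive calls is conditional on pooling the implants. At a single visit it is material for proteins detected on about 0.5% to 5% of strips. Across all seven visits it is small unless detection is about 1% or less. These figures assume independent strips with equal detection at every site; the documents give no detection rate.

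**What to change.** 1. Define three groups for the proteome: tooth, conventional implant and PEMF implant. Build the protein lists from complete triplets, so that each group has the same number of strips.
2. Make the functional comparison a per-participant score for each term, compared in pairs (PEMF v conventional; tooth v conventional) at each visit, with false-discovery-rate control across terms. Keep the top-ten list as description only.
3. If enrichment is used, apply it to proteins that differ between groups, with all proteins identified in this study as background. Over-representation within each group does not compare PEMF with conventional. For the 12-protein term above, all present in a group holding 400 of 500 proteins, it gives a hypergeometric p = C(488,388)/C(500,400) = 0.066 before any correction for 200 terms.
4. Prespecify a minimum detection frequency before a protein is called exclusive, for example 8 of 40 participants at a visit, with a sensitivity check at other cut-offs. The 8 is a convention, not a derived value.

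The cost is more analysis time on the same files and fewer proteins called exclusive. No extra samples or readings are needed.
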